1.1 Background

Age-related macular degeneration (AMD) is the leading cause of severe vision loss in people over the age of 65 in the United States and other Western countries (Rein et al., 2009). The neovascular, exudative or wet form of AMD (nAMD) is characterized by the growth of abnormal new blood vessels (neovascularization) under the retinal pigment epithelium (RPE) from the choroid into the retina (Ferris et al., 1984). These newly formed vessels have an increased likelihood to leak blood and serum, damaging the retina by stimulating inflammation and scar tissue formation which results in progressive, severe, and irreversible vision loss (Shah and Del Priore, 2007, Shah and Del Priore, 2009). Without treatment, most affected eyes will have poor central vision (20/200) within 12 months (Blinder et al., 2003).

Vascular endothelial growth factor (VEGF) was identified to play a key role in the neovascularization process (Spilsbury et al., 2000). The use of intravitreal injection pharmacotherapy targeting VEGF, such as ranibizumab (Lucentis®) and aflibercept (Eylea®), has significantly improved visual outcomes in patients with nAMD (Bloch et al., 2012, Campbell et al., 2012) and has been shown to halt the growth of neovascular lesions and resolve retinal edema, which raised anti-VEGF treatments to current standard of care in nAMD.

Brolucizumab

Brolucizumab is a humanized single-chain antibody fragment (scFv), binding to VEGF-A with high affinity. It works by binding to the receptor binding site of the VEGF-A molecule, thereby preventing the interaction of VEGF-A with its receptors VEGFR1 and VEGFR2 on the surface of endothelial cells (Escher et al., 2015). Brolucizumab has a molecular weight of ~26 kDa which allows a delivery of a high molar dose via intravitreal injection. A 6 mg dose of brolucizumab delivers a molar dose which is approximately 11 and 22 times higher than aflibercept 2 mg and ranibizumab 0.5 mg, respectively. Higher molar doses are expected to lead to longer presence of relevant drug levels in the eye. In addition, a low molecular weight and high concentration gradient between the vitreous and the retina may increase drug distribution to the target site of action, supporting effective control of anatomical disease activity and has therefore the potential to show superior outcomes.

Brolucizumab has been approved for treatment of nAMD by more than 70 health authorities globally, e.g. the Food and Drug Administration (FDA), the European Medicines Agency (EMA) and Swissmedic. It was tested in two large phase 3 trials and found to be efficacious and safe when compared to aflibercept in patients with nAMD (HAWK and HARRIER). Brolucizumab demonstrated non-inferiority to aflibercept in mean change in best-corrected visual acuity (BCVA) from baseline to week 48 in both trials. Treatment of treatment-naïve patients was started with three monthly brolucizumab injections (loading phase), followed by treatment every 12 weeks (q12w). If disease activity was identified during the study, patients were assigned to treatment every 8 weeks (q8w) and stayed on the q8w interval until the end of study. After one year of treatment, the primary endpoint was met with change of BCVA from baseline being non-inferior with more than 50 % of patients (56 % in HAWK, 51 % in HARRIER) were being maintained on a q12w dosing interval following the loading phase through week 48 in the brolucizumab arm vs. the aflibercept arm (fixed q8w treatment frequency). The visual acuity gains observed in the first year were maintained in the second

year. In addition, in these phase 3 trials brolucizumab demonstrated superior anatomical outcomes vs. aflibercept. Significantly fewer patients on brolucizumab had intraretinal fluid (IRF) and/or subretinal fluid (SRF) and brolucizumab achieved superior reductions in central subfield thickness (CSFT) versus aflibercept. These superior anatomic outcomes for brolucizumab were maintained in the second year. Brolucizumab safety was comparable to aflibercept, with the overall incidence of adverse events balanced across all treatment groups in both studies.

Since the first marketing authorization approval in October 2019 for the treatment of nAMD, adverse events of retinal vasculitis and/or retinal vascular occlusion, that may result in severe vision loss and typically in the presence of intraocular inflammation, have been reported from post-marketing experience with brolucizumab (Beovu). Results of the mechanistic study BASICHR0049 on blood samples from nAMD patients exposed to brolucizumab and having subsequently developed retinal vasculitis and/or retinal vascular occlusion, taken together with accumulated data from HAWK, HARRIER and MERLIN, regarding the association of treatment-emergent immunogenicity and intraocular inflammation (IOI), indicate a causal link between the treatment-emergent immune reaction against brolucizumab and the brolucizumab-related retinal vasculitis (RV) and/or retinal vascular occlusion (RO), typically in the presence of IOI. This finding supports the requirement to discontinue treatment with brolucizumab in patients who develop events of RV and/or RO.

In addition, based on the USM (CRTH258AUS04, MERLIN, first interpretable results [FIR]), the interval between two brolucizumab doses should not be shorter than 8 weeks beyond the loading phase.

These impacts on the risk/benefit balance of the product are considered to be low and the overall risk/benefit assessment remains positive, when patients are dosed at q8w or longer after the loading phase and when patients who develop RV and/or RO are discontinued from further treatment with brolucizumab.

Current standard therapy regimens

Currently marketed anti-VEGF treatments typically start with a loading phase of 3 monthly doses, followed by maintenance dosing, either with fixed (e.g. every 4 or 8 weeks) or individualized treatment intervals, based on *pro re nata* (PRN) or Treat-and-Extend (T&E) concepts (Wykoff et al., 2018).

In ranibizumab and aflibercept trials, in both interventional (e.g. TREND (Silva et al., 2018), ALTAIR (Bayer Vital GmbH, 2019) and real life studies (prospective non-interventional trials, e.g. OCEAN (Voegeler and Mueller, 2017), a number of patients still showed persistent fluid when extended to q6w or longer treatment intervals, although initial functional and anatomical response after the loading phase (three initial injections) was seen. The German Retina Society recommends that switching to another anti-VEGF drug may be considered if an inadequate morphological effect is observed after the initial three series or follow-up therapies. In several case series it was shown that after a change of the drug, a further visual stabilization could be achieved with a simultaneous reduction of the morphological lesion activity criteria (Retinologische Gesellschaft, 2014).

For these patients, a presumably more effective and longer lasting anti-VEGF agent like brolucizumab may lead to optimized fluid, and disease control i.e. sustained functional and anatomical response, respectively; which overall might result in improved patient care (e.g. less frequent visits, reduced treatment burden). Often the switch is initiated with a loading phase of three monthly doses, as described above for treatment naïve patients. However, a clear recommendation and scientific evidence is missing and it is unclear how to optimally initiate the change to brolucizumab treatment subsequent to an unsatisfactory anti-VEGF treatment response.

Summary

Ranibizumab, aflibercept and brolucizumab all inhibit the activity of VEGF-A and all have demonstrated efficacy in the treatment of patients with nAMD. However, under ranibizumab and aflibercept, a number of patients have still shown persistent fluid when extended to q6w or longer treatment intervals. Since brolucizumab showed superior anatomical outcomes and longer durability in HAWK & HARRIER, these findings support the evaluation of brolucizumab also in pretreated patients.

1.2 Purpose

The purpose of this study is to evaluate the efficacy and safety of two different brolucizumab 6 mg treatment regimens for pretreated patients with suboptimal anatomically controlled nAMD. We aim to evaluate whether nAMD patients who showed an unsatisfactory response to previous anti-VEGF treatments (i.e. residual or recurrent fluid despite continuous anti-VEGF treatment), can immediately go to a q12w regimen when treatment is initiated with brolucizumab 6mg, or need loading with three monthly brolucizumab 6 mg injections. Our goal is to provide insights to support the medical practice and put the results of our descriptive analysis into context together with current and future literature on how to treat patients who had an unsatisfactory response to other anti-VEGF treatments.

2 Objectives and endpoints

As a consequence of Amendment 2, the assumed patient number necessary for analysis of the primary objective will not be achieved. Therefore, the primary endpoint and all analyses will now be performed in a purely descriptive manner.

Table 2-1 Objectives and related endpoints

Objective(s)	Endpoint(s)
Primary Objective(s)	Endpoint(s) for primary objective(s)

To evaluate the difference in brolucizumab 6 mg with one (initial) injection followed by q12w maintenance as compared to brolucizumab 6 mg with 3x q4w loading injections followed by q12w maintenance	
Mean change in BCVA from baseline to mean of visits at week 40 to week 52
Secondary Objective(s)	Endpoint(s) for secondary objective(s)

Objective(s)	Endpoint(s)

• To evaluate treatment interval prolongation compared to previous treatment• To estimate the proportions of patients maintained at q12w treatment frequency in the two brolucizumab groups• To evaluate the functional outcomes comparing the two brolucizumab groups• To evaluate the anatomical outcomes comparing the two brolucizumab groups• To evaluate the safety and tolerability of brolucizumab	
• Mean treatment interval (overall as well as per study group comparing treatment intervals from baseline to week 52 in the study vs. 24 weeks to baseline prior to enrollment)• Rate of patients (overall and per group) with prolonged interval compared to mean treatment interval in last 24 weeks prior to enrollment• Comparison of proportions of patients maintained at a q12w interval at week 52 between the two arms• Distributions of patients at q8w/q12w intervals from baseline to week 52• Average change in BCVA from baseline to week 52• Proportions of patients with BCVA improvements of ≥ 5, ≥ 10, and ≥ 15 letters from baseline to week 52• Proportions of patients with BCVA ≥ 69 letters at week 52• Mean change in BCVA from baseline to mean of visits at week 16 to week 28• Change from baseline in CST as assessed by SD-OCT per visit up to week 52• Absence of IRF, SRF, and sub-RPE fluid as assessed by SD-OCT per visit up to week 52• Presence of active CNV leakage as assessed by fluorescein angiography at week 52• Incidence of ocular and non-ocular AEs up to week 52

3 Study design

This study is a 52-week randomized, open-label, multi-center, two arm study for pretreated patients with suboptimal anatomically controlled nAMD. Patients who consent will be screened whether they meet all the inclusion and none of the exclusion criteria to evaluate eligibility. After confirmation of eligibility, patients will be randomized in a 1:1 ratio to one of the two treatment arms:

- Brolucizumab 6 mg “**loading arm**”: 3 x 4-weekly initial injections followed by an injection every 12 weeks;
- Brolucizumab 6 mg “**non-loading arm**”: one initial injection followed by an injection every 12 weeks

The initial plan was to screen approximately 598 adult patients (18 % screening failure rate expected) and randomize approximately 490 patients (245 per arm, 10 % drop-out rate expected) in a 1:1 ratio in approximately 65 centers. According to Amendment 2 for premature discontinuation of recruitment, the planned sample size will not be achieved, expecting a total of approximately 50 patients to be recruited by the time of approval of Amendment 2 (25 per arm, in approximately 33 centers).

The maximum study duration for one subject is 54 weeks, including the screening period and post-treatment follow-up.

There will be three periods in this study (see [Figure 3-1](#) and [Figure 6-2](#)):

- Screening period: from day -14 to baseline
- Open-label treatment period: from baseline (day 1) to week 48
- Post-treatment follow-up period: from week 48 to week 52

[figure not shown]

Figure 3-1 **Study design**

1. Screening period: Day -14 to day -1

A screening period of up to 2 weeks will be used to assess eligibility.

One-time rescreening of patients is allowed, **except** for the purpose of capturing new BCVA or imaging assessments that previously failed to qualify the patient. As long as testing can be repeated within 14 days of the first screening, the other screening assessments do not need to be repeated. If rescreening is to occur beyond 14 days from the original screening visit date, then all screening procedures must be repeated. Medical judgment should be exercised to ensure that treatment of nAMD is not withheld in order for a patient to participate in the study.

2. Open-label treatment period: Day 1 to week 48

After confirmation of eligibility, patients will be randomized in a 1:1 ratio to one of the treatment arms.

Only one eye will be selected as study eye and treated with study medication.

The baseline visit is defined as day 1/visit 1, and end of treatment visit as visit 13 (week 48).

A study visit schedule will be established at the time of randomization for all patients with study visits scheduled every 4 weeks. All efforts should be made to adhere to this study visit schedule \pm 7-day window. Treatment is intended to be administered on the day of study visit, or if this is not possible, within 3 days after the study visit when the per-protocol assessments took place. In addition, for a given protocol visit, assessments can be performed in two consecutive days.

In the “loading arm”, patients will receive three consecutive injections every 4 weeks at baseline, weeks 4 and 8, which should be at least 21 days apart, followed by an injection every 12 weeks. In the “non-loading arm”, patients will receive one initial injection followed by an injection every 12 weeks. For both study arms: The assessment of disease activity will be performed 8 and 12 weeks after the previous injection. If disease activity is identified by the investigator for the first time at any visit after / from week 8 respectively, patients should stay on a q12w dosing, if the decline in BCVA is clinically non-significant (BCVA loss \leq 4 ETDRS letters) compared to the previous visit. If after / from week 8, a BCVA-loss of \geq 5 ETDRS letters appears compared to the previous visit or disease activity is identified for a second time based on the investigator’s judgment of visual and/or anatomic outcomes and signs of disease activity, patients must be assigned to q8w dosing. One attempt of interval re-extension from q8w to q12w treatment will be allowed based on the investigator’s judgement if no disease activity (DA) is detected during the subsequent visit(s). If the patient shows significant DA at any visit after the re-extension attempt, injection intervals will be fixed to q8w until the end of the study. The disease activity decision should be based on the BCVA loss criteria (BCVA loss \leq 4 ETDRS letters and BCVA-loss of \geq 5 ETDRS compared to the previous visit) and beyond that on investigator’s judgement of visual and/or anatomic outcomes and signs of disease activity (e.g. IRF, SRF, hemorrhage, leakage, visual acuity loss over time etc.).

Patients who require injections more frequently than every 8 weeks after the loading phase (week 8, loading arm) or baseline (non-loading arm) will be discontinued from further study treatment.

3. Post-treatment follow-up period: Week 48 to week 52

For all patients, the last study assessment will be performed at week 52.

Patients withdrawn from the study prior to study completion will be asked to return for an early discontinuation visit (EOS / visit 14), four weeks (\pm 7 days) following their last study visit (see [Section 9](#)).

4 Rationale

4.1 Rationale for study design

This study is designed as a randomized, open-label, multi-center, two-arm parallel study to assess the efficacy and safety of two different brolucizumab 6 mg regimen for pretreated patients with suboptimal anatomically controlled nAMD.

The primary efficacy endpoint based on BCVA was chosen to evaluate the benefits of treatment in terms of functional outcome. Non-inferiority testing was intended originally related to the primary efficacy parameter BCVA change from baseline. However, due to feasibility reasons, purely descriptive analyses will be performed. Historically, the change from baseline in BCVA at a selected time point is considered appropriate as the primary efficacy endpoint in confirmatory nAMD studies, based on the evidence available from existing anti-VEGF treatments in nAMD (e.g. ranibizumab, aflibercept). The BCVA assessment has its own variability and generally in the clinical practice a change of BCVA ≥ 5 letters would be considered as clinically relevant regardless of the underlying disease.

The BCVA will be evaluated as the mean change from baseline to mean of visits at week 40 to 52 due to the fact, that patients will receive injections at different intervals and timepoints. Patients in the loading arm on a q12w treatment interval may receive their last injection at week 44, whereas patient in the non-loading arm on a q12w treatment interval may receive their last injection at week 48. Shifting from q12w to a q8w treatment regime will also lead to differences in treatment schedule. A difference in the time since the last injection between both arms may affect BCVA gain and could introduce a bias on BCVA gain if measured at a single fixed assessment time point. Averaging change in BCVA from baseline at four time points 12 weeks apart will mitigate this potential bias.

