6.7.2 Instruction for prescribing and taking study treatment

There will be two different treatment regimens (see [Figure 6-2](#)) for IVT injections with different timing for brolucizumab “loading” and “non-loading” treatment arms:

- **Brolucizumab 6 mg “loading”:** Treatment with brolucizumab will be initiated with three loading injections every 4 weeks for three consecutive injections (baseline, weeks 4 and 8). From week 8 onwards, patients will be scheduled to receive one injection of brolucizumab 6 mg every 12 weeks.
- **Brolucizumab 6 mg “non-loading”:** Treatment with brolucizumab will be initiated with one single injection (baseline). From baseline onwards, patients will be scheduled to receive one injection of brolucizumab 6 mg every 12 weeks.

For both study arms:

- The assessment of disease activity will be performed 8 and 12 weeks after the previous injection.
- If disease activity is identified by the investigator for the first time at any visit after / from week 8 respectively, patients should stay on a q12w dosing, if the decline in BCVA is clinically non-significant (BCVA loss \leq 4 ETDRS letters) compared to the previous visit.
- If after / from week 8, a BCVA-loss of \geq 5 ETDRS letters appears compared to the previous visit or disease activity is identified for a second time based on the investigator’s judgement of visual and/or anatomic outcomes and signs of disease activity*, patients must be assigned to q8w dosing.
- One attempt of re-extension to q12w will be allowed based on the investigator’s judgement if no disease activity (DA) is detected during the subsequent visit(s).
- If the patient shows significant DA after the re-extension attempt, injection intervals will be fixed to q8w until the end of the study

- *The disease activity decision should be based on the BCVA loss criterium (BCVA loss ≥ 5 ETDRS letters or ≤ 4 ETDRS letters compared to the previous visit) and beyond that on investigator's judgment of visual and/or anatomic outcomes and signs of disease activity (e.g. IRF, SRF, hemorrhage, leakage, visual acuity loss over time etc.).

[figure not shown]

Figure 6-2 Treatment regimen

Evaluation of Disease Activity (DA):

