The concept of the brolucizumab q12w/q8w regimen is to allocate patients according to their individual treatment needs to either a q12w or a q8w treatment schedule. The initial schedule is q12w and a patient will remain on q12w as long as the investigator does not identify nAMD disease activity which in his opinion requires more frequent anti-VEGF treatment (BCVA-loss of ≥ 5 ETDRS letters compared to the previous visit or disease activity is identified for a second time based on the investigator's judgement of visual and/or anatomic outcomes).

In case of BCVA-loss of ≥ 5 ETDRS letters compared to the previous visit, the patient must be switched to a q8w regimen. Beyond the BCVA loss criteria, the assessment of the DA is at the discretion of the investigator and should be made based on changes in vision and anatomical parameters (e.g. IRF, SRF, hemorrhage, leakage, vision loss over time etc.) with reference to the patients' disease status. [Figure 6-3](#) shows three examples for regimen adjustments for the loading arm (examples 1-3) and non-loading arm (examples 4-6), respectively.

[figure not shown]

Figure 6-3 Examples for treatment regimen adjustments

Brolucizumab should be administered in the study eye on the day of the study visit or, if this is not possible, within 3 days after the occurrence of the study visit or no later than within the visit window (± 7 days) as described in [Section 3](#) and [Section 8](#). Every effort should be made to ensure that the subject adheres to the visit/treatment schedule.

When assessments and treatments take place on the same day, treatment must occur after completion of the efficacy assessments described in [Section 8.3](#) and pre-injection safety measures (tonometry, slit lamp and fundus examinations) described in [Section 8.4.3](#). If study visit assessments and the corresponding treatment occur on separate days, a repeat safety checkup should be performed prior to treatment of the eye and results documented in the source documents. If any safety concern arises related to the study eye that, in the opinion of the investigator, may be further impacted by the study treatment or injection procedure, treatment needs to be cancelled.

Brolucizumab administration

The IVT injection procedure for brolucizumab including aseptic and antimicrobial requirements, will be performed according to local clinical practice. IVT injection is contraindicated in

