5.4 Statistical models

5.4.1 Primary analysis

1) SAS-Code for **mixed model for repeated measures (MMRM)**:

Estimates for the primary objective ("Mean change in BCVA from baseline to mean of visits at week 40 to week 52 (Visit 11 to 14)") and the secondary objective ("Mean change in BCVA from baseline to mean of visits at week 16 to week 28 (Visit 5 to 8)") in one single model:

```
proc mixed alpha=0.1;
  where fasfl=Y and trteyen=1;
  where 2 le avisitn le 14;
  class subjid trtan avisitn;
  model chg = base age trtan avisitn trtan*avisitn /ddfm=kr;
  repeated avisitn / sub = subjid type = un;
  lsmeans trtan*avisitn /slice = avisitn cl ;
  estimate 'Treatment difference averaged over week 40 to week 52'
    trtan -1 1
    trtan * avisitn
      0 0 0 0 0 0 0 0 -0.25 -0.25 -0.25 -0.25
      0 0 0 0 0 0 0 0 0.25 0.25 0.25 0.25/cl;
  estimate 'Treatment difference averaged over week 16 to week 28'
    trtan -1 1
    trtan * avisitn
      0 0 0 -0.25 -0.25 -0.25 -0.25 0 0 0 0 0 0
      0 0 0 0.25 0.25 0.25 0.25 0 0 0 0 0 0/cl;
run;
```

3) SAS-Code for **logistic regression** model:

- Secondary endpoint: "rate of patients (overall and per treatment arm) with prolonged interval (*intlong*) compared to mean treatment interval in last 24 weeks prior to enrollment"

```
proc logistic descending alpha=0.05;
  where fasfl=Y;
  class trtan;
  model intlong = base age trtan;
run;
```

- Secondary endpoint: "proportions of patients maintained at a q12w interval from baseline / upload to week 52"

```
proc logistic descending alpha=0.05;
  where fasfl=Y;
  class trtan;
  model q12w = base age trtan;
run;
```

where 'maintained at a q12w interval' (q12w = Yes) is defined as DAA = q12w in all visits AND no treatment discontinuation.

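### Equal weighting of weeks 40 to 52 reduces the time-since-injection imbalance between arms, but leaves one nominal week of it (8.0 versus 7.0 weeks) among patients on q12w

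*Protocol*

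**What the plan says.** Protocol 4.1 explains that patients reach the end of the study at different times after their last injection. In the loading arm, "Patients in the loading arm on a q12w treatment interval may receive their last injection at week 44"; the sentence goes on, "whereas patient in the non-loading arm on a q12w treatment interval may receive their last injection at week 48". It recognises that this difference could bias a comparison made at one visit, and gives the remedy: "Averaging change in BCVA from baseline at four time points 12 weeks apart will mitigate this potential bias".

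The calendars are set in Protocol 6.7.2. For the loading arm, after injections at baseline and weeks 4 and 8: "From week 8 onwards, patients will be scheduled to receive one injection of brolucizumab 6 mg every 12 weeks". For the non-loading arm: "From baseline onwards, patients will be scheduled to receive one injection of brolucizumab 6 mg every 12 weeks". Protocol Section 3 has "study visits scheduled every 4 weeks". BCVA is measured before any injection given at the same visit: "When assessments and treatments take place on the same day, treatment must occur after completion of the efficacy assessments".

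SAP 5.4.1 defines the primary contrast as the treatment difference averaged over visits 11 to 14 (weeks 40 to 52), with equal weights of 0.25. The first row of visit coefficients reads "0 0 0 0 0 0 0 0 -0.25 -0.25 -0.25 -0.25". The same model gives the weeks 16 to 28 contrast, also with weights of 0.25. Neither document tabulates time since injection or notes that the first and last visits of each window share a phase of the q12w cycle.

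**The concern.** Four visits 4 weeks apart span 12 weeks with both ends included. They cover one q12w cycle and then repeat its first phase. Because the arms' calendars are offset, the repeated phase differs between them. Equal weighting therefore cannot balance time since injection exactly.

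The trial asks whether loading can be omitted. If vision fades between 4 and 8 weeks after injection, the leftover imbalance favours the non-loading arm. It is systematic, so a larger sample would not reduce it, and the results are meant to be read alongside other literature.

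**Working it through.** **Inputs.**
- q12w injection weeks (Protocol 6.7.2): loading 0, 4, 8, 20, 32, 44; non-loading 0, 12, 24, 36, 48. These reproduce the last injections given in Protocol 4.1, weeks 44 and 48.
- Endpoint visits: weeks 40, 44, 48, 52.
- Time since injection at a visit = visit week minus the last injection week strictly before it, because BCVA precedes treatment.
- Planning precision (Protocol 12.8.1): SD 13 letters, 25 per arm. 1.96 × 13 × √(2/25) = 7.207, which reproduces the stated 7.21.

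**Step 1. Weeks since injection on q12w.**

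| Visit week | Loading | Non-loading | Loading minus non-loading |
|---|---|---|---|
| 40 | 8 | 4 | +4 |
| 44 | 12 | 8 | +4 |
| 48 | 4 | 12 | −8 |
| 52 | 8 | 4 | +4 |
| Equal-weight mean | 8.0 | 7.0 | +1.0 |

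Weeks 16, 20, 24 and 28 give the same rows: 8/12/4/8 and 4/8/12/4, means 8.0 and 7.0.

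**Step 2. Bias in letters.** Let f(t) be the BCVA effect t weeks after injection, assumed common to both arms. Non-loading minus loading is

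¼[f(4) + f(8) + f(12) + f(4)] − ¼[f(8) + f(12) + f(4) + f(8)] = ¼[f(4) − f(8)].

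At week 52 alone it would be f(4) − f(8). Averaging leaves one quarter of that, whatever the shape of f.

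**Step 3. Size.** The documents give no value for f(4) − f(8), so 1 to 3 letters is an assumption.
- All patients on q12w: 0.25 × 1 = 0.25 to 0.25 × 3 = 0.75 letters.
- A patient on steady q8w is seen at 8/4/8/4 or 4/8/4/8 weeks, mean 6.0 either way, and adds no imbalance in phase. If 51 to 56% of each arm stay on q12w (the shares Protocol 4.5 reports from two phase 3 trials; using them here is an assumption), the bias is 0.51 × 0.25 = 0.13 to 0.56 × 0.75 = 0.42 letters.
- Against the half-width of 7.21 letters, 0.25 to 0.75 is 3 to 10%, and 0.13 to 0.42 is 2 to 6%.
- With q8w shares pL (loading) and pN (non-loading), mean times are 8 − 2pL and 7 − pN, so the gap is 1 − 2pL + pN weeks. Equal q8w shares of 44 to 49% give 0.56 to 0.51 weeks.

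**Step 4. Alternative weights 1/6, 1/3, 1/3, 1/6.**
- Loading: 8/6 + 12/3 + 4/3 + 8/6 = 8.0. Non-loading: 4/6 + 8/3 + 12/3 + 4/6 = 8.0.
- Each of the 4-, 8- and 12-week phases carries weight one third in both arms, so the imbalance vanishes for any f. Steady q8w stays balanced: the 4- and 8-week phases carry one half each.
- Precision: the sum of squared weights rises from 0.250 to 10/36 = 0.278. Under compound symmetry with correlation ρ (an assumption), the SE ratio is √{[ρ + 0.278(1 − ρ)] / [ρ + 0.250(1 − ρ)]}, which is 1.008 at ρ = 0.6 and 1.002 at ρ = 0.9.

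**The case against.** A reader might infer that Protocol 4.1 makes a false claim, or that the endpoint fails in its purpose. The text does not support that. It says the bias is mitigated, not removed. The mean gap falls from 4 weeks at week 52, or 8 weeks in the other direction at week 48, to 1 week.

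A reader might also set 0.25 to 0.75 letters against the 5-letter change that Protocol 4.1 calls clinically relevant and report a 5 to 15% tilt. That goes too far. The fade is assumed, and the range applies only if every patient stays on q12w. The interval rule also works against a large fade: a loss of at least 5 letters from the previous visit moves a patient to q8w, and at the 8-week assessment the previous visit falls 4 weeks after injection. Patients still on q12w late in the study are therefore likely to be those with little fade over just that interval.

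The analysis is descriptive, with no margin or test for a fraction of a letter to tip. The endpoint is defined as the mean of the visits, which equal weights implement. Visit windows (±7 days, ±21 days at week 52) and injections up to 3 days after a visit mean that 8.0 versus 7.0 describes the calendar, not observed times.

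All of this limits size and severity. The calendar imbalance still stands. A wide interval reflects random error and is no reason to leave a known systematic difference unreported when showing its effect costs almost nothing.

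**Conclusion.** The point holds as a small residual. Equal weighting does what Protocol 4.1 claims, but leaves a nominal 1-week difference in time since injection among q12w patients, in both the weeks 40 to 52 and the weeks 16 to 28 contrasts. The 8.0 versus 7.0 weeks and the factor of one quarter follow exactly from the nominal schedule. The size in letters does not: it rests on an assumed fade, an effect curve common to both arms, and assumed q12w shares. On those assumptions it is below one letter, and probably below half a letter. The direction, favouring non-loading, holds only if vision does fade between 4 and 8 weeks, and with unequal q8w shares the gap in mean weeks could vanish or reverse. Low severity: the primary endpoint remains usable and no planned conclusion depends on this.

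**What to change.** Keep the planned equal-weight contrasts. In the same MMRM, add two supplementary ESTIMATE statements with weights 1/6, 1/3, 1/3, 1/6, one for weeks 40 to 52 and one for weeks 16 to 28, and report each beside its planned counterpart. Each arm needs 13 visit coefficients, for visits 2 to 14. In the text available for this review, each printed row for the planned weeks 40 to 52 contrast has only 12, while the weeks 16 to 28 rows have 13. This may be a loss in text extraction, so check it against the signed SAP and the program.

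In Protocol 4.1, or in a note in the SAP if the protocol is not reopened, keep the word mitigate, state that a 1-week difference remains on q12w, and describe the visits as 4 weeks apart spanning 12 weeks.

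The cost is two statements and a sentence or two, with an SE increase below 1% at the assumed correlations. The drawback is a second version of each estimate to report. Exact balance holds for steady q12w and steady q8w on the nominal calendar, but not for patients who change interval within the window or are seen off schedule.
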